## 9.2 Operational definitions for (S)AEs, (S)ARs and SUSARs

(S)AEs, (S)ARs and SUSARs will be defined according to standard definitions, section 9.1.

## 9.3 Recording and reporting of SAEs, SARs and SUSARs

SAEs, S(AR)s and SUSARS will be recorded on case report forms (CRFs).

Non-serious AEs will not be reported to YTU and will not be recorded on CRFs.

SAEs/SARs will be reported to YTU, except for exemptions detailed below, via e-mail using a form provided by YTU within 24 hours of the research team becoming aware of the event. SAEs which are exempt from reporting to YTU are those which occur commonly in this patient population, as follows:

- Infections including surgical wound infections, respiratory, urinary and skin infections (including fungal infections).
- Surgical complications such as failure of a surgical procedure (specifically anastomotic breakdown or development of a fistula) or bowel obstruction. Deterioration of the existing condition specifically progression of a cancer.
- Treatment which was elective or pre-planned, for a pre-existing condition not associated with any deterioration in condition, e.g. pre-planned hip replacement operation which does not lead to further complications.
- Any admission to hospital or other institution for general care where there was no deterioration in condition.
- A full list of specific SAEs which do not need to be reported is available in Appendix 6.

Non-serious ARs will not be reported to YTU and will not be recorded on CRFs.

SARs will be reported to YTU, except for specific exemptions, via e-mail using a form provided by YTU within 24 hours of the research team becoming aware of the event. SARs exempt from reporting to YTU are those where reporting will not improve the knowledge regarding the safety profile of the drug, i.e., if the event or reaction is listed as a known event within the drug's SmPC.

SUSARs will be reported to YTU via e-mail using a form provided by YTU within 24 hours of the research team becoming aware of the event. All SAEs assigned by the PI or delegate (or following central review) as both suspected to be related to IMP-treatment and unexpected will be classified as SUSARs and will be reported by YTU to the Medicines and Healthcare Products Regulatory Agency (MHRA) via the yellow card scheme within 1 working day.

For each SAE / SAR/ SUSAR the following information will be collected:

- full details of the event
- seriousness criteria
- event duration (start and end dates, if applicable)
- outcome
- action taken
- causality (i.e. relatedness to trial drug / investigation), in the opinion of the investigator
- whether the event would be considered expected or unexpected.

Any change of condition or other follow-up information should be e-mailed to YTU as soon as it is available on a follow-up report form provided by YTU, or at least within one working day of the information becoming available. Events will be followed up until resolved or a final outcome reached.

YTU will be responsible for reviewing all reported **SAEs / SARs / SUSARs**. Where they are to be reported to the sponsor, YTU will email reports to [contact] within 1 working day of becoming aware of the event.

#### 9.4 Responsibilities

#### Principal Investigator (PI):

Checking for AEs and ARs when participants attend for treatment / follow-up.

- Using medical judgement in assigning seriousness, causality and expectedness using the Reference Safety Information approved for the trial. The reference information sheet for the trial is each drug's SmPC.
- 2. Report SAEs and SARs to YTU within 24 hours.

#### Chief Investigator (CI) / delegate or independent clinical reviewer:

- 1. Clinical oversight of the safety of patients participating in the trial, including an ongoing review of the risk / benefit.
- 2. Using medical judgement in assigning seriousness, causality and expectedness of SAEs where it has not been possible to obtain local medical assessment.
- 3. Using medical judgement in assigning expectedness.
- 4. Clinical review of a line listing of all life threatening or SAEs resulting in death within 1 week of their occurrence.
- 5. Clinical review of a line listing of all other SAEs on a monthly basis (for lower risk trial).
- 6. Immediate review of all SUSARs.

#### Sponsor responsibilities (delegated to YTU)

- 1. Central data collection and verification of SAEs, SARs and SUSARs according to the trial protocol onto a database.
- 2. Reporting safety information to the CI, delegate or independent clinical reviewer for the ongoing assessment of the risk / benefit according to the Trial Monitoring Plan.
- 3. Ensuring that where relevant SAEs and SARs (including SUSARs) are recorded and reported to the sponsor within 1 working day of becoming aware of the event and provide further follow-up information as soon as available. Ensuring that reported SAEs and SARs (including SUSARs) are chased with Sponsor if a record of receipt is not received within 3 working days of initial reporting.
- 4. Reporting safety information to the independent oversight committees identified for the trial (DMEC and / or TSC) according to the Trial Monitoring Plan.
- 5. Expedited reporting of SUSARs to the Competent Authority (MHRA in UK) and REC within required timelines.
- 6. Notifying Investigators of SUSARs that occur within the trial.

## Trial Steering Committee (TSC):

In accordance with the Trial Terms of Reference for the TSC, periodically reviewing safety data and liaising with the DMEC regarding safety issues.

## Data Monitoring and Ethics Committee (DMEC):

In accordance with the Trial Terms of Reference for the DMEC, periodically reviewing overall safety data to determine patterns and trends of events, or to identify safety issues, which would not be apparent on an individual case basis.

## 9.5 Notification of deaths

Death is considered as a SAE and will be reported to the sponsor in line with SAE reporting.

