#### Assessment

The PI or a delegated medic assess whether the adverse event is serious (SAE) or not (AE). An SAE is any untoward medical occurrence that fits one or more of the below criteria:

- results in death
- is life-threatening
- requires inpatient hospitalisation or prolongation of existing hospitalisation
- results in persistent or significant disability/incapacity
- consists of a congenital anomaly or birth defect

AE - reporting to YTU is not required.

SAE

Does the event meet one or more of the below criteria:

Infections including surgical wound infections, respiratory, urinary and skin infections (including fungal infections).

- Surgical complications such as failure of a surgical procedure (specifically anastomotic breakdown or development
  of a fistula) or bowel obstruction. Deterioration of the existing condition specifically progression of a cancer.
- Treatment which was elective or pre-planned, for a pre-existing condition not associated with any deterioration in condition, e.g. pre-planned hip replacement operation which does not lead to further complications.
- Any admission to hospital or other institution for general care where there was no deterioration in condition.

No

The clinical team report the serious adverse event (SAE) on an an EXTEND trial SAE form. The PI or a delegated medic is responsible for assessing whether the SAE is due to the trial treatment, and whether it is expected for the antibiotic the patient received.

If the event is definitely, probably or possibly related and is unexpected, the SAE form must be sent to YTU immediately following review to [contact]. Otherwise, the SAE form should be sent to YTU within 24 hours of study site staff becoming aware of the event.

Any change of condition or other follow-up information should be entered on an SAE follow-up form and emailed to YTU as soon as it is available, or at least within one working day of the information becoming available. Events will be followed up until resolved or a final outcome reached.

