# **NHS** Health Research Authority

## Appendix 6 – A full list of specific SAEs which do not need to be reported

#### CARDIAC

Arrhythmia Cardiac arrest Myocardial Infarction or ischaemia

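### Deaths follow the SAE reporting route, but that route exempts events by type without saying whether the exemption holds when the event is fatal

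*Protocol*

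**What the plan says.** Section 9.5 is the only section devoted to deaths: "Death is considered as a SAE and will be reported to the sponsor in line with SAE reporting". It gives no separate form, timeline or list.

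Section 9.3 sets out the SAE route: "SAEs/SARs will be reported to YTU, except for exemptions detailed below, via e-mail using a form provided by YTU within 24 hours". On the exemptions it says: "SAEs which are exempt from reporting to YTU are those which occur commonly in this patient population". It then names infections, surgical complications, cancer progression, elective treatment and admission for general care, and refers to Appendix 6 for the full list. Appendix 6 opens its cardiac group with "Arrhythmia Cardiac arrest Myocardial Infarction or ischaemia". Further on it lists sepsis, respiratory failure, pulmonary embolism, stroke, bowel infarction, gastrointestinal bleed and progression of the underlying condition, among others.

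The Appendix 5 flow chart first decides whether an event is serious, with a fatal result as one criterion. It then asks: "Does the event meet one or more of the below criteria". In the text of the chart, the SAE form and the assessment of causality and expectedness follow a No.

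Section 9.4 gives the Chief Investigator or delegate this task: "Clinical review of a line listing of all life threatening or SAEs resulting in death within 1 week of their occurrence".

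**The concern.** The rule for deaths points to a route that removes events by diagnosis, and the removed diagnoses include several that can be fatal in these patients. No exemption is limited to non-fatal events. A site that applies section 9.3 and Appendix 6 as written could conclude that a death from sepsis or respiratory failure needs no 24-hour SAE form. Section 9.4 assumes the opposite, because fatal SAEs can be listed and reviewed within a week only if they have been reported.

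What is at stake is prompt safety oversight of deaths: an early judgement on relatedness, notification of the sponsor, and a complete list for the one-week review. The point has weight here because the intervention is longer antibiotic exposure, and Appendix 6 also exempts gastrointestinal tract infection, acute kidney injury, allergy and expected drug reactions. A fatal event of one of these kinds is one that early review should see.

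**Working it through.** The point rests on reading the sections together. Arithmetic only sets the scale.

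**1. Following a fatal event through the text**

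| Step | Source | Result for a fatal event of an exempt type |
|---|---|---|
| Is it an SAE? | 9.1, 9.5, Appendix 5 | Yes |
| Which route? | 9.5 | The ordinary SAE route |
| Does that route have exemptions? | 9.3 | Yes, by event type |
| Are they limited to non-fatal events? | 9.3, Appendix 6 | Not stated |
| Is death itself on an exemption list? | 9.3, Appendix 6 | No |
| Must fatal SAEs be reviewed centrally within a week? | 9.4 | Yes |
| When does the sponsor hear? | 9.3, 9.4 | After the trials unit becomes aware, so it depends on the site's report |

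The fourth and fifth rows pull in opposite directions and nothing in the text settles them. If the exemptions apply to fatal events, the listing needed for the sixth row is incomplete.

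**2. The two appendices compared**

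The chart in Appendix 5 repeats only the general categories of section 9.3. Infections (and so, arguably, sepsis), anastomotic breakdown, fistula, bowel obstruction and cancer progression are on it. Cardiac arrest, stroke, respiratory failure, pulmonary embolism and bowel infarction are not, and the chart's text does not refer to Appendix 6. A site using the chart alone would report a fatal cardiac arrest. A site using Appendix 6 could treat it as exempt.

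**3. What is captured in any case**

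Section 9.3 has SAEs recorded on case report forms, and its exemption concerns reporting to the trials unit only. Section 11.1 has case report form data entered directly on the trial database, which the trials unit hosts. Section 3.6 has all-cause mortality assessed at day 180 from records and interview. The death is therefore captured, but no deadline comparable to 24 hours or one week attaches to those sources. In the UK observational study cited in section 1 the median time to death was 23 days. If that applied here from randomisation (an assumption), the day-180 assessment would come 180 − 23 = 157 days after a typical death.

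**4. Scale**

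Inputs: planned sample size 1166 (section 10.1); mortality 11.3% in the UK observational study and 10 to 20% in broader populations (section 1). The sample size is consistent with its own inputs: 524 / 0.9 = 582.2, rounded up to 583 per arm, and 2 × 583 = 1166.

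Expected deaths = 1166 × mortality:
- 1166 × 0.113 = 131.8, about 132
- 1166 × 0.10 = 116.6, about 117
- 1166 × 0.20 = 233.2, about 233

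The protocol gives no causes of death, so the share with an exempt cause is an assumption. The table shows deaths that could fall outside the 24-hour form if the exemptions are taken to cover fatal events.

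| Mortality | 25% exempt | 50% | 75% | 90% |
|---|---|---|---|---|
| 10% | 29 | 58 | 87 | 105 |
| 11.3% | 33 | 66 | 99 | 119 |
| 20% | 58 | 117 | 175 | 210 |

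The range of 29 to 210 is too wide to serve as an estimate. It shows only that the number need not be trivial.

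**The case against.** The best reply is that section 9.5 already makes every death reportable. It has its own heading, it calls death itself an SAE, and the exemption lists name diagnoses rather than outcomes. On that reading the reference to SAE reporting means the same form and timeline, and sections 9.4 and 9.5 agree. This may well be the intent. It is not stated, however, and nothing in section 9.3 or either appendix tells a site to set an exempt diagnosis aside because the patient died.

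Other parts of the reply limit the point, and they stand:

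- A reader might infer that deaths would be unknown to the trials unit. The documents do not support that, given case report form recording and the mortality outcome. Only the expedited step is in question.
- A reader might infer that the DMEC would not see mortality by arm. That does not follow. The protocol gives the committee unblinded safety data and critical efficacy endpoints, and what else it receives is left to terms of reference and a monitoring plan that are not at hand.
- A reader might say that the Appendix 5 chart exempts cardiac arrest, or that it has no branch for deaths. The first is wrong on its text. The second cannot be asserted, because the chart is available only as extracted text and part of its structure is missing.
- Section 9.3 states no exemption for SUSARs. That helps, but a SUSAR is identified through causality and expectedness, which the chart's text places after the exemption question.

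**Conclusion.** The concern holds as an unresolved contradiction in the safety reporting text. Section 9.5 relies on a route whose exemptions, read literally, can remove fatal events, while section 9.4 requires those events to be reviewed within one week. Expedited causality assessment, notification of the sponsor and completeness of the one-week listing are at risk. Knowledge of the death and the mortality analysis are not.

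About 132 deaths are expected at 11.3% mortality, and 117 to 233 at 10 to 20%, assuming the cited rates carry over to this trial. A reader might go on to say that most deaths would escape SAE reporting. The breadth of Appendix 6 makes that tempting, but without cause-of-death data it cannot be shown. It would also require sites to apply the exemptions to fatal events, which the protocol leaves open. No sample size, error rate or efficacy analysis is affected.

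**What to change.** Reconcile sections 9.3, 9.4 and 9.5 and Appendices 5 and 6:

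1. State in section 9.3, and repeat in Appendices 5 and 6, that the reporting exemptions do not apply to an event that results in death.
2. Align the exemption list in the Appendix 5 chart with Appendix 6, so that a site reaches the same answer from either.
3. Have the sponsor reconcile the status of life-threatening events. Section 9.4 includes them in the one-week review, yet several exempt types can be life-threatening. Lifting the exemption for all of them would be a real trade-off in a trial that recruits from intensive care and deliberately exempts common events, so it is not proposed here.

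The cost is a short amendment and one additional SAE form for each death from an otherwise exempt cause. That number cannot be predicted from the documents, but it cannot exceed the total number of deaths.

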## 9.6 Pregnancy reporting

Pregnancy is not considered an AE and will not be reported.

## 9.7 Reporting urgent safety measures

An "urgent safety measure" is a procedure which is not defined by the protocol that can be put in place with immediate effect without needing to gain prior authorisation by the REC (and MHRA where applicable), in order to protect clinical trial participants from any immediate hazard to their health and safety.

If any urgent safety measures are taken by an investigator, these must be reported to YTU within 24 hours. YTU will take responsibility for reporting of urgent safety measures to the Sponsor (if not already aware), MHRA (if applicable) and the relevant REC if required.

## 10 STATISTICS AND DATA ANALYSIS

## 10.1 Sample size calculation

The primary outcome for this study is treatment failure. Using an estimated proportion of treatment failure in the standard treatment group of  $\geq$  50% over the 180 days of follow up, an effective sample size of 1048 patients (524 per arm) obtains 90% power to detect a 10% (absolute) reduction in incidence of the clinical outcome in a two-sided test of size 5%. Assuming 10% attrition 1166 patients (583 per arm) are required. The sample size calculation was carried out using Stata version 16.0.

## 10.2 Statistical analysis plan

## 10.2.1 Statistical analysis overview, principles and procedures

Analyses will be conducted following ITT principles and will follow a detailed pre-specified statistical analysis plan (SAP) completed and approved during the internal pilot phase, and prior to any review of the outcome data. All analyses will be conducted just once at the end of the trial, with no modification of trial processes (including termination) being made based on interim comparisons of accumulating outcome data (hence no stopping rules/monitoring boundaries are specified). Any deviations from the pre-specified analyses in the SAP will be detailed according to YTU's standard operating procedures.

The flow of patients through the trial will be reported in a CONSORT diagram, including the number of patients screened (and reasons for ineligibility), the number approached for consent (and reasons for non-consent), the number randomised, adherence to allocated treatment, follow-up data completeness and the number of participants included in the analyses. Descriptive summaries of

continuous data (or discrete numerical data with many distinct values) will be given in terms of the non-missing sample size, arithmetic mean, standard deviation, median, inter-quartile range, minimum and maximum. Descriptive summaries of categorical data (or discrete numerical data with few distinct values) will be given in terms of frequencies and proportions.

All analysis models used to compare treatment strategies will include all randomised participants with data available for the relevant outcome in the groups to which they were allocated (unless explicitly stated otherwise). For binary outcomes, differences between randomised groups will be estimated on the log odds scale, conditional on informative baseline covariates (including the randomisation stratification factors) unless otherwise stated. Point and interval estimates of conditional odds ratios will be reported. Point and interval estimates of relative risk (cases/non-cases) and absolute risk reduction based on estimated marginal effects from these models will also be reported. For ordinal categorical outcomes, differences between randomised groups will be estimated on the log odds scale, conditional on informative baseline covariates (including the randomisation stratification factors), using appropriate ordinal logit models (unless otherwise stated). Point and interval estimates of the conditional odds ratios obtained from the fitted models will be reported. For continuous and count outcomes, differences between groups will be estimated using appropriate generalised linear models, with the differences between groups (absolute or relative) obtained from the fitted models being reported on the scale of the original measurements, unless stated otherwise.

#### 10.2.2 Baseline data

Baseline data will be collected immediately prior to randomisation and will include the variables described in Section 7.5. These data will be reported by group (and overall), as randomised (i.e. including baseline data from all randomised patients) and as included in the primary analysis (i.e. including baseline data from all participants with non-missing primary outcome data). Reporting of these data will be descriptive (see detailed specification of statistics reported in Section 10.2.1), with no interval estimation or testing of differences in baseline characteristics being conducted or reported. In addition to the tabular summaries described above, plots of the distribution of key baseline characteristics will also be generated.

#### 10.2.3 Primary outcome analysis

The primary clinical outcome is treatment failure (Failure vs No failure) within 180 days of randomisation, as defined in Section 3.4. The number and proportion of participants experiencing treatment failure will be reported by randomised group and overall, as will the number of participants with complete outcome and covariate data. The primary analysis will model the log odds of treatment failure using a mixed effect logistic regression model, with randomised treatment group, the stratification factors (Post-operative vs Non post-operative cIAI, Source control vs No source control,

ICU care vs No ICU care), and other pre-specified prognostic baseline covariates included as fixed effects, and random intercepts for recruitment site/hospital. All participants with non-missing primary outcome data will be included in this model, with any missing baseline covariate data being imputed using an appropriate method prior to model fitting. Inference concerning the effectiveness of the intervention will be primarily based on the estimated conditional odds ratio, two-sided 95% confidence interval and p-value for allocation from the fitted primary analysis model. To aid interpretability, point estimates and appropriate two-sided 95% confidence intervals for the relative risk (cases/non-cases) and absolute risk reduction (based on the fitted primary analysis model) will be reported, with the fixed effect covariates in the model set to various representative values (i.e. marginal risk ratio and risk difference at representative values). Average marginal effects on both the risk ratio and risk difference scales will also be reported with appropriate two-sided 95% confidence intervals.

Several pre-specified sensitivity analyses of the primary outcome will be conducted to investigate the possible influence of non-adherence (via the estimation of alternative estimands that aim to account for non-adherence), and different assumptions about the missing outcome data (via analysis of data multiply imputed assuming outcome data are missing at random (MAR) and assuming various systematic departures from MAR).

